A pilot study was conducted to compare the effectiveness of pharmacopuncture and physiotherapy in patients with chronic LBP. The between-group difference in the mean reduction of the NRS score for LBP was 1.37 ± 1.94 at the primary endpoint, which is immediately after the 5-week treatment; further, Cohen's d was calculated as 0.71. The correlation between the baseline and endpoint was 0.53. Given a significance of 95% and power of 90%, the sample size was calculated to be 64. Considering a 30% withdrawal rate and the recruitment of participants from four facilities, we aim to recruit 100 patients.

Recruitment

Participants will be recruited using a press release, advertisement posters at the clinical trial facility, and online recruitment sites.

Randomization and Allocation Concealment

A statistician will randomize patients into two groups at the same ratio (50 persons for each) using a randomization table on R studio 1.1.463 (© 2009-2018 R Studio, Inc.). The random sequence will be performed using block randomization; further, the size of each block will be randomly set to 2 or 4. The randomization results will be placed in a sealed opaque envelope and stored in a double-locked cabinet by a third person not involved in the study. The coordinator at each study facility will open the envelope for group allocation. Only participants who provide an ICF will be randomly assigned. The randomization number assigned to each participant will be recorded in the electronic medical record.

Blinding

Since blinding the practitioner administering the treatment and the participants is impossible due to the nature of the intervention, only the outcome assessors will be blinded. Outcome-assessors not involved in the procedure and blinded from the group allocation will perform the assessment before the procedure in an isolated space.

Data Collection and Management

We will use an e-CRF using the Internet-based Clinical Research and Trial management system (iCReaT). The principal investigator will train the outcome assessors and investigators of each facility on the standard operating procedure (SOP) as a reference for the study procedures, including writing a CRF and entering data. A query will be issued for a range check of data values. Data entered into the e-CRF will be cleaned and locked to prevent access by investigators other than the one in charge of data management.

Statistical Methods

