We will perform both intention-to-treat (ITT) and per-protocol (PP) analyses, with ITT as the primary analysis. For the PP analysis, we will include participants who complete at least seven treatment sessions over 5 weeks. Missing data will be handled by multiple imputation (MI) for analysis of covariance (ANCOVA) and comparison of area under the curve (AUC), as well as

the mixed model for repeated measures for the linear mixed model. For survival analysis, outcomes after the missing time point will be censored. For sensitivity analysis, the last observation carried forward (LOCF) will be used for missing data imputation; further, the normality of distribution will be tested. Nonparametric data will be analyzed using the Wilcoxon-rank sum test. Sociodemographic characteristics and treatment expectancy of the participants will be assessed according to the group. Continuous variables will be presented as mean (SD) or median (quartile), with between-group differences being analyzed using Student's t-test or Wilcoxon-rank sum test, depending on their distribution. Categorical variables will be presented as frequency (%) and analyzed with the chi-square test or Fisher's exact test.

The study endpoints are the differences in the extent of changes in continuous outcomes (NRS, VAS, NDI, NPQ, EQ- 5D-5L, SF-12) at each time point from the baseline. As the primary analysis, we will use a linear mixed model with the covariant factors significantly different from the baseline as covariates and the group as the fixed factor. Next, ANCOVA will be performed on sets processed by MI and LOCF.

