To compare the total difference in each outcome within a certain period (treatment period and total study period), the AUC will be calculated for each time point after randomization and compared using Student's t-test. Further, the proportion of patients whose NRS and VAS scores dropped by > 50% from the baseline values will be compared at each time point. The time from randomization to lumbar recovery, which was defined as > 50% reduction in the pain indices, will be compared using Kaplan-Meier survival analysis. Further, the curves will be compared using the Log rank test. Additionally, hazard ratios will be compared using the Cox proportional hazard model. The significance level will be set at 0.05 for all analyses. All statistical analyses will be performed using the SAS 9.4 (© SAS Institute, Inc., Cary, NC, USA) or R studio 1.1.463 (© 2009-2018 RStudio, Inc.) software. Statistical significance will be set at $p < 0.05$.

In case the superiority test fails, a non-inferiority test will be performed. The non-inferiority margin will be set to -1 (NRS), which represents half of the minimal clinically important difference. Pharmacopuncture will be considered non-inferior to physiotherapy if the lower bound of the 95% confidence interval (CI) of the between-group difference of the NRS score reduction does not exceed the non-inferiority margin.

Data Monitoring

The monitoring staff will supervise the clinical trial process, as well as periodically review and confirm whether the study is performed and recorded according to the protocol, SOP, clinical trial management standards, and applicable regulations. The clinical trial will be monitored by the monitoring staff of each clinical trial facility and the sponsor institution using periodic visits and phone calls. At the monitoring visits, the monitoring staff will check the original participant records and data storage (study files). Further, they will inspect the clinical trial procedure and discuss any problems with the investigators.

In case of unexpected or unacceptable risks to participants or occurrence of serious adverse events related to pharmacopuncture or physiotherapy in $\geq 25\%$ of the participants, the clinical trial may be paused. The analysis will be only accessed by the statistician and principal investigator; additionally, the final decision to terminate the study will be made by the principal

investigator

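### The censoring rule for time to recovery is not limited to permanent withdrawal, so read as written it discards recoveries seen after a patient misses an assessment and returns

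*Combined protocol and SAP*

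**What the plan says.** All the relevant text is in the Statistical Methods section of the combined protocol and SAP.

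- **Event.** "The time from randomization to lumbar recovery, which was defined as > 50% reduction in the pain indices", "will be compared using Kaplan-Meier survival analysis". A log-rank test follows, and "hazard ratios will be compared using the Cox proportional hazard model".
- **Missing data for this analysis.** One sentence, which says that for the survival analysis "outcomes after the missing time point will be censored". Nothing else says how a patient who misses an assessment and comes back is handled, or that censoring is at the last attended assessment.
- **Missing data elsewhere.** ANCOVA and AUC use multiple imputation, and the linear mixed model handles missing values as a mixed model for repeated measures. LOCF is a sensitivity analysis.
- **Responder analysis.** Separately, "the proportion of patients whose NRS and VAS scores dropped by > 50% from the baseline values will be compared at each time point".
- **Analysis set.** Both ITT and per-protocol, "with ITT as the primary analysis".

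**The concern.** The trigger in the sentence is a missing time point, not withdrawal or loss of contact, and what it removes is whatever comes afterwards. An analyst who follows it literally ends a patient's follow-up at the first gap, even when later pain scores are in the database.

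Recovery status is known only at assessments. A skipped one makes the date of recovery less exact, but it does not make a recovery recorded later unknown.

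The rule is also out of step with the rest of the plan. The mixed model, the imputation-based analyses and the responder proportions all use a returning patient's later scores. The same patient could count as a responder at a later time point and be censored without recovery in the survival curve.

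Two things are at stake. The first is lost events, and with them precision in the log-rank and Cox comparisons. The second is possible bias if missing a visit relates to pain or differs between arms. That is plausible here: the Blinding section says that patients and practitioners know the allocation, and the Concomitant Treatment section allows outside care for severe pain.

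**Working it through.** **Figures in the plan.** No figure is given for the time-to-recovery analysis. The only design figure is the total of 64 in Sample Size Calculation, for the NRS endpoint, where the difference "was 1.37 ± 1.94 at the primary endpoint" and the baseline–endpoint correlation is 0.53. It reproduces:

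- adjusted SD = 1.94 × √(1 − 0.53²) = 1.645
- standardized difference = 1.37 / 1.645 = 0.833
- a t-test at two-sided 5% (assumed two-sided) with 90% power needs 31.29 per arm, rounded up to 32, or 64 in total

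This does not bear on the censoring rule.

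**Reading the rule on one patient.** Suppose assessments 1 and 2 are attended without recovery, 3 is missed, and 4 is attended with pain more than halved.

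- Under the sentence as written, the patient is censored at the gap and the event is not counted.
- If all attended assessments are used, the event is counted at assessment 4.
- If the patient never returns after assessment 2, both readings censor and nothing observed is lost.
- If recovery was already recorded before the gap, both readings keep it.

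**Illustration of size (all inputs assumed).** V is the number of assessments (6 or 10), p the chance of missing each one independently (0.03 or 0.10), and h the chance of first recovering at each one (0.10 or 0.20). Recovery persists and there is no dropout.

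- Recovery first occurs at assessment k with probability h(1−h)^(k−1).
- It is kept under the literal rule if assessments 1 to k are all attended: (1−p)^k.
- It is observable if at least one of assessments k to V is attended: 1 − p^(V−k+1).
- Share lost = 1 − [Σ h(1−h)^(k−1)(1−p)^k] / [Σ h(1−h)^(k−1)(1−p^(V−k+1))].
- Usable follow-up is cut if the first miss is at assessment j, recovery has not been seen before j, and a later assessment is attended: Σ p(1−p)^(j−1)(1−h)^(j−1)(1−p^(V−j)).

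| V | p | h | Observable per 100 | Kept per 100 | Recoveries lost | Patients with usable follow-up cut |
|---|---|---|---|---|---|---|
| 6 | 0.03 | 0.10 | 46.7 | 42.6 | 8.8% | 11.6% |
| 6 | 0.03 | 0.20 | 73.6 | 67.7 | 8.0% | 9.6% |
| 6 | 0.10 | 0.10 | 46.2 | 34.0 | 26.4% | 33.8% |
| 6 | 0.10 | 0.20 | 73.0 | 55.3 | 24.2% | 28.5% |
| 10 | 0.03 | 0.10 | 65.0 | 56.7 | 12.7% | 16.6% |
| 10 | 0.03 | 0.20 | 89.2 | 79.8 | 10.6% | 12.0% |
| 10 | 0.10 | 0.10 | 64.7 | 41.6 | 35.7% | 44.5% |
| 10 | 0.10 | 0.20 | 89.0 | 61.9 | 30.4% | 33.8% |

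On the planned 100 patients, the gap between observable and kept recoveries runs from about 4 (46.7 − 42.6) to about 27 (89.0 − 61.9).

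**Second set of assumptions.** A simulation with 5 to 12 assessments, recovery probability 0.08 to 0.12 per assessment and 2% to 10% missed gave losses of about 5% to 40%. With 8 assessments, 5% missed and recovery probability 0.12, it gave 63.9 recoveries observed per 100 and 53.0 kept, a loss of 1 − 53.0/63.9 = 17%.

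**The case against.** The strongest reply is that the authors meant dropout. The sentence speaks of a single missing time point, and the only missingness that the document quantifies is the 30% withdrawal rate in Sample Size Calculation. If missingness is always permanent, the sentence is ordinary right-censoring and discards nothing. That stands as a possible intention, so a reader should not infer that this trial is certain to lose recoveries. But the text does not say so, and it leaves the treatment of a returning patient to whoever writes the program.

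The illustration also leans towards a larger effect. If pain fluctuates, a later visit may not show the recovery. Missed visits in practice tend to cluster in a few patients, which lowers the share affected. Withdrawals cost no observed events under this rule. The upper end needs ten assessments with 10% missed at each. All of this stands, and the range is not a forecast.

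Three stronger readings are tempting but unsupported:

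- **That 17–65% of patients lose follow-up.** This is 1 − (1−p)^V, from 1 − 0.97^6 = 16.7% to 1 − 0.90^10 = 65.1%. It is the chance of missing any assessment, including one missed after recovery is already recorded, when nothing is lost.
- **That the hazard ratio is biased.** Nothing in the documents shows that missed visits relate to pain or arm. If they do, censoring non-returners at their last attended assessment is informative too, so the fix reduces this risk without removing it.
- **That the survival methods must be replaced.** Observing recovery only at assessments is a separate matter. Counting later recoveries cures this defect within the planned Kaplan-Meier, log-rank and Cox analyses.

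**Conclusion.** The point holds as a defect in the wording of one rule for a secondary analysis. As written, the rule removes recoveries first observed after an intermittent gap, although the plan uses the same scores elsewhere. The certain cost, wherever patients miss an assessment and return recovered, is lost events and precision. Bias is a possibility only.

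The size cannot be taken from the documents. Under the tabulated assumptions it is about 8–36% of observable recoveries, with 9.6–44.5% of patients having usable follow-up cut. It is zero if every missing assessment is part of permanent dropout. A reader might infer that the main result is threatened, but the primary NRS analysis is a linear mixed model that does not use this rule, and the sample size is untouched. The point is a desirable clarification, not a serious fault.

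**What to change.** Replace the censoring sentence in Statistical Methods with:

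> Patients without an observed recovery are censored at their last attended assessment. A missed assessment followed by an attended one does not censor, and a recovery first seen at a later attended assessment counts as an event at that assessment.

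This costs one sentence. It needs no new data, no change to the sample size and no change to the planned methods or software. The small downside is that a recovery after a gap is dated less exactly, at the assessment where it is seen. If that matters, an interval-censored analysis, placing recovery between the last attended assessment without it and the first with it, can be added as an optional sensitivity analysis.

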Pharmacopuncture therapy will be given two times a week for five weeks. With reference to a study on the current trend in pharmacopuncture therapy that used electronic medical records from 12 Korean medical hospitals,¹¹ the treatment will be performed following the physician's clinical judgment. Additionally, all procedure-related matters will be recorded in patients' charts. Pharmacopuncture procedures will be retrospectively reviewed and recorded in a case report form (CRF) for analysis.

Control Group: Physiotherapy

Based on a study on HIRA data, patients with LBP in Korea are treated using a combination of deep heat therapy, superficial heat therapy, transcutaneous electrical nerve stimulation, and intermittent pelvic traction therapy.¹² According to this data, a physician will choose the method, site, and duration of physiotherapy based on their clinical judgment with respect to the patients' symptoms, radiological findings, and improvement levels. Physiotherapy will be performed twice a week for five weeks; further, all matters regarding the physiotherapy, including the type, duration, and site of physiotherapy, will be recorded in patients' charts. The treatment method will be retrospectively reviewed and recorded in CRF for comparison.

Criteria for Discontinuation and Withdrawal

A participant may be discontinued from the clinical trial for the following reasons: Discovery of a previously undetected disease that may affect study outcomes Request for discontinuation during the study period by the participant or their legal representative or withdrawal of consent by the participant Confirmation of pregnancy during the study period Problems regarding the administration of medical and Korean medical procedures for LBP to the participant Other reasons that warrant discontinuation from the study as determined by the researcher

Concomitant Treatment

Pharmacological therapy and medical care for LBP from another healthcare facility may be permitted during the treatment or follow-up period in case of severe pain. The treatment details and frequency will be recorded in the CRF for analysis.

Outcome

Primary Outcome

NRS score of LBP

The LBP intensity within the previous week will be assessed using the NRS. Patients will be instructed to choose a number from 0–10 that best represents their current discomfort level (0 for no pain, 10 for the worst imaginable pain).

Secondary outcomes

NRS score of radiating leg pain

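### LOCF is the only missing-data sensitivity analysis, so the plan cannot show how far dropouts must depart from missing at random before its superiority or non-inferiority conclusion changes

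*Combined protocol and SAP*

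**What the plan says.** All of the missing-data plan is in Statistical Methods. The primary analysis is a linear mixed model in the ITT population, with a repeated-measures mixed model named as its way of dealing with missing values. MI is named for the ANCOVA and the AUC comparison, without an imputation model. The sensitivity analysis is then given: "For sensitivity analysis, the last observation carried forward (LOCF) will be used for missing data imputation". The order of analysis is completed by "Next, ANCOVA will be performed on sets processed by MI and LOCF". A per-protocol analysis takes participants with at least seven sessions, and the time-to-event analysis censors at the missing time point.

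The same section adds a fallback: "In case the superiority test fails, a non-inferiority test will be performed". Its margin is -1 on the difference in NRS reduction, described as half the minimal clinically important difference (MCID), which implies an MCID of 2. No analysis set, model or missing-data method is named for that test.

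Three other sections bear on dropout:
- Sample Size Calculation: "Considering a 30% withdrawal rate", 100 patients are to be recruited.
- Blinding: "Since blinding the practitioner administering the treatment and the participants is impossible due to the nature of the intervention", only the outcome assessors are blinded. The primary NRS is the patient's own rating.
- Criteria for Discontinuation and Withdrawal: the listed reasons include "Request for discontinuation during the study period by the participant or their legal representative".

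**The concern.** The mixed model is valid under MAR. So is MI by default, and the plan states no shift or other departure. Agreement between the two therefore says little about MAR itself. The per-protocol set changes who is analysed, not what is assumed about missing scores. Censoring concerns only the time-to-event outcome. That leaves LOCF, which freezes each dropout's score at the last value and has no parameter to vary.

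Patients who know their treatment, rate their own pain and may leave on request could drop out for reasons tied to pain that is never recorded, in either arm. If many week-5 scores are missing, a superiority or non-inferiority conclusion would then rest on MAR with no measure of how large a departure it can bear.

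**Working it through.** **Inputs from the documents.** Sample Size Calculation: difference in mean NRS reduction 1.37, SD 1.94, baseline-endpoint correlation 0.53, 90% power, 64 evaluable, 30% withdrawal. Randomization and Allocation Concealment: 50 per arm. Statistical Methods: margin -1, 95% CI.

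**Assumed, not in the documents.** The share p of week-5 scores missing in each arm. The penalty delta, in NRS points, added to a dropout's imputed score (more pain, smaller reduction). The share f of the final change already present at a dropout's last score. A control-arm mean reduction of 2 to 3 points.

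**1. The plan's own figure.** Residual SD = 1.94 × √(1 − 0.53²) = 1.645. With two-sided 0.05 and a noncentral t, power is 89.7% at 31 per arm and 90.6% at 32, so 32 per arm gives the stated 64. Then 64/0.70 = 92 after rounding up, and the plan recruits 100. Using 1.94 without adjustment gives 86, so 1.645 is the SD that fits the plan.

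**2. Tipping points, penalty on pharmacopuncture dropouts only (normal approximation).** The estimate falls by p × delta. SE = 1.645 × √(2/(50(1 − p))). Superiority from 1.37 is lost at (1.37 − 1.96 SE)/p. Non-inferiority from an observed 0 is lost at (1 − 1.96 SE)/p.

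| p | SE | 1.96 SE | Superiority from 1.37 | Non-inferiority from 0 |
|---|---|---|---|---|
| 10% | 0.347 | 0.68 | 6.9 | 3.2 |
| 20% | 0.368 | 0.72 | 3.2 | 1.4 |
| 30% | 0.393 | 0.77 | 2.0 | 0.76 |

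MI with Rubin's rules at 30% gives slightly smaller values, 1.79 and 0.65. With SD 1.94 the 30% row would be 1.54 and 0.30.

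The last column is for one observed difference only. At 30% missing, superiority fails and non-inferiority holds for any observed difference D from 0.77 − 1 = -0.23 up to 0.77. Over that range the tip is (D + 1 − 0.77)/0.30: 0 at -0.23, 0.76 at 0, 1.6 at 0.25, 2.4 at 0.5 and 3.3 at 0.77.

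**3. Penalties in the other arm.** In general the shift is −p(pharmacopuncture) × delta(pharmacopuncture) + p(physiotherapy) × delta(physiotherapy). By MI at 30% missing, starting from 1.37:
- 2 points on pharmacopuncture only: 0.77 (95% CI -0.07 to 1.61)
- 2 points on physiotherapy only: 1.97 (1.13 to 2.81)
- 2 points on both: 1.37 (0.49 to 2.25)

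With 40% v 20% dropout, 2 points on both shifts the estimate by (0.4 − 0.2) × 2 = 0.4, against whichever arm loses more patients.

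**4. Which way LOCF leans.** With equal dropout the expected LOCF difference is (1 − p + p × f) times the true one. At p = 30% the factor is 0.70 for f = 0 and 0.85 for f = 0.5. A true -1 becomes -0.70 or -0.85, and a true 1.37 becomes 0.96 or 1.16. In 20,000 simulated trials with the truth at -1, false non-inferiority was 12% to 16% at f = 0 and about 7% at f = 0.5, against a nominal 2.5%.

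With unequal dropout the direction changes. Take 40% dropout on pharmacopuncture v 20% on physiotherapy, a true -1 and f = 0. With a control reduction of 2, LOCF gives 1 × 0.6 − 2 × 0.8 = -1.0. With a control reduction of 3 it gives 2 × 0.6 − 3 × 0.8 = -1.2. False non-inferiority was then 0.6% to 2.6% over f = 0 and 0.5. With the dropout rates reversed, the LOCF difference was -0.2 to -0.7 and false non-inferiority 17% to 58%.

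**The case against.** A reader might infer that LOCF favours the non-inferiority claim as a matter of course. The documents do not support that. The lean needs similar dropout by arm, or more on physiotherapy, together with a difference still developing and pharmacopuncture truly worse. The pilot points to pharmacopuncture being better. In that case, with equal dropout, LOCF moves the estimate down toward -1, which works against non-inferiority. With clearly more pharmacopuncture dropout LOCF is neutral or leans against non-inferiority.

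A reader might also infer that the non-inferiority result will itself be computed on LOCF data. Statistical Methods does not say so. LOCF is a sensitivity set beside a primary mixed model, so any bias falls on the robustness check.

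Nor is 30% a forecast of missing week-5 scores; it is a planning allowance. At 10% missing, a penalty of 6.9 points is needed to overturn superiority from 1.37. Even at 30%, the superiority tip of about 2.0 points, applied to one arm only, equals the implied MCID, which is reasonably robust. Finally, MAR for the MI is a default reading, because no imputation model is given.

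All of this stands and limits the point. It does not supply what is missing: no planned analysis varies the departure from MAR. That the direction of LOCF turns on an unknown dropout pattern is itself a reason not to rely on it alone.

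**Conclusion.** The concern holds as a gap in the robustness evidence, and the primary analysis is not invalidated. How much it matters depends on how many week-5 scores are missing. At about 10% it is small. At 30% per arm, superiority at the planned effect would survive a one-arm penalty up to roughly the MCID, while a non-inferiority conclusion could be anywhere from fragile to robust depending on the observed difference. LOCF cannot tell these cases apart. The figures rest on residual SD 1.645, equal dropout in the tipping-point table, and the normal approximation; the LOCF figures also rest on assumed f and control-arm reductions. The stated sample size reproduces and is not affected.

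**What to change.** Make delta-adjusted MI, applied to the planned MI-ANCOVA for week-5 NRS, the sensitivity analysis for missing data.
- First confirm that at delta 0 it agrees with the primary mixed model, so that the tipping point speaks to the primary result.
- Add delta to imputed scores separately in each arm, on a fixed grid of 0.5-point steps from 0 to at least 2 points. Cap imputed scores at 10; do not stop the grid when a score reaches 10.
- Report the estimate and 95% CI for every pair of deltas, judged against 0 and against -1.
- Define the tipping point as the smallest delta in one arm, with the other arm at 0, that changes each conclusion, or state that none does within the grid.
- Apply the same grid to the non-inferiority test. This also requires saying which analysis set and model that test uses.
- LOCF may stay as a supplementary analysis but should not be offered as support for non-inferiority.

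The cost is a few SAP sentences and a short extra run on imputed sets already planned. No new data are needed, and neither the primary analysis nor the sample size changes. The downside is less prominence for LOCF, which older trials reported.
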